11.3.4. Summary of PK Concentrations

For PK concentration summary, the following rules apply:

- PK concentrations BLQ in pre-dose samples and in samples taken before the time of the first quantifiable value are set to zero;
- The PK concentrations BLQ after quantifiable concentration are set to zero;
- · The sampling time of pre-dose samples relative to dosing will be treated as zero;
- Drug concentrations will be summarized by nominal time point;
- Descriptive statistics will be performed;
- No further imputation is applied to any missing values.

Plasma MP1032 concentrations will be summarized descriptively by study day, time point and treatment (in relevant concentration units) using descriptive statistics (n, number and percent of patients with BLQ, arithmetic mean, geometric mean, SD, arithmetic and geometric coefficient of variation (CV) %, minimum, median and maximum) presented according to the following reporting precision.

Variable	Summarized with:
Minimum, Maximum	3 significant digits or as needed based on actual measured values
Arithmetic Mean, Geometric Mean, Median	4 significant digits or as needed based on actual measured values
SD	5 significant digits or as needed based on actual measured values
CV%, and Geometric CV%	1 decimal place or as needed based on actual measured values

Mean ± SD plasma concentration-time profiles for MP1032 of all patient on linear and log-linear scales will also be presented.

11.4. PK Parameters Derivation

For the derivation of PK, the following rules will apply:

- All plasma concentrations BLQ will be imputed with a value of zero;
- The sampling time of pre-dose samples relative to dosing will also be treated as zero;
- Actual blood sampling times will be used to derive PK parameters. If the actual blood sampling is
 not present, then that time point will not be considered for PK analyses.

This document is confidential.

SAP Text Version: 2.0, 31-Aug-2022 Controlled Document ID: CC , Effective Date 31-Aug-2020 Filing requirements: TMF

Page 41 of 56

- If the pre-dose sample is not present, then that patient will not be considered for PK derivation;
- No further imputation will be applied to any missing values.

All PK parameters will be listed.

11.4.1. PK Parameters Summarization

PK parameters and concentrations data will be summarized using the following descriptive statistics:

Variable	Summarized with:
PK concentration at each time point	n, arithmetic mean, SD, coefficient of variance (CV) %, minimum, median and maximum
AUCs, Cmax, Ctrough, CL/F, and $V_{\rm Z}/F$	n, arithmetic mean, SD, CV%, minimum, median, maximum, geometric mean and geometric CV%
T _{%el} , K _{el}	n, arithmetic mean, SD, CV%, minimum, median, maximum
t _{max} (actual time)	n, minimum, median, and maximum

Note: CV% = SD/mean in %; n = No. of observations.

For PK tables and listings, the final reportable results or data will be presented by rounding off to two decimal digits, except for the following situations (this applies to individual data and descriptive statistics):

- Kel and Rsq adjusted data: rounded off to four decimal digits.
- Pharmacokinetic parameters related to time such as t_{max}, K_{el Lower}, and K_{el Upper} must be reported with the same precision as the actual sampling time: rounded off to 3 decimal digits.

Concentration versus time data: reported as they appear in corresponding dataset.

11.5. Exploratory Relationship between Plasma exposure, and Biomarker (Exposure-Response relationship)

Any possible correlation between plasma exposure (C_{max}, or AUC_D-t) and biomarkers (eg, change from baseline in cytokines, or other coagulation/inflammatory biomarkers) using Day 7 if available, may be explored applying exposure-response scatterplots. Further correlation analysis (eg, utilizing a combination of Spearman and Pearson correlation) may be applied if exposure-response scatterplots reveal any robust relationships. Tables will be then produced for calculated correlation coefficient, confidence intervals for Pearson coefficient in addition to p-value, to demonstrate the validity of correlation.

This document is confidential.

SAP Text Version: 2.0, 31-Aug-2022 Controlled Document ID: CCI , Effective Date 31-Aug-2020 Filing requirements: TMF

Page 42 of 56

12. Pharmacodynamics

Biomarker levels potentially including, but not limited to, cytokines (eg, C-reactive protein, interleukin [IL]-1 β , IL-6, tumor necrosis factor- α , and IFN- γ), and other coagulation/inflammatory biomarkers (eg, D-dimer and ferritin) will be summarized by actual values and changes from baseline by treatment group and visit on the SS. The change in biomarker levels will be evaluated with any change of COVID-19 clinical status by presenting summary tables of the change in biomarker levels from baseline stratified by COVID-19 status by treatment group.

This document is confidential.

SAP Text Version: 2.0, 31-Aug-2022 Controlled Document ID: CC , Effective Date 31-Aug-2020 Filing requirements: TMF

Page 43 of 56

13. Safety

The population used for safety analyses will be the Safety Set (SS). Safety will be assessed based on adverse event (AE) or adverse drug reactions (ADR) reports, clinical laboratory data, ECG parameters, physical examinations, and vital signs.

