This document is confidential.

SAP Text Version: 2.0, 31-Aug-2022 Controlled Document ID: CCC , Effective Date 31-Aug-2020 Filing requirements: TMF

Page 20 of 56

- 1. For WOCBP, a serum sample for pregnancy testing must be collected at screening and a urine sample for pregnancy testing must be collected before the first dose on Day 1. Pregnancy tests must be negative for the patient to be randomized and treated. A urine pregnancy test will be repeated on Day 14 (± 7 days). If the patient is discharged before Day 14, urine pregnancy test at day of discharge should be done, and urine pregnancy test at Day 14 is not required. If the patient is discharge after Day 14, urine pregnancy test at day of discharge is not required test should be done at Day 14, and urine pregnancy test at day of discharge is not required (whichever comes first). Patients with a positive pregnancy test will be discontinued from study drug.
- m. Only for patients discharged before Day 28. If the patient does not feel comfortable to complete the diary, the site will alternatively provide the patient with the option to be called, twice a day, to confirm that the study drug is taken as instructed.
- n. Plasma PK samples will be collected via sparse sampling from approximately 30 patients (who give optional consent) in a 2:1 ratio to assess the PK of MP1032 on Day 1 (single dose) and Day 7 (steady state). A total of 16 samples will be collected relative to the first dose on Day 1 and the first dose on Day 7. Samples on Day 1 and Day 17 will be collected predose (within 10 minutes before the first daily dose) and postdose at 10 minutes, 20 minutes, 30 minutes, 60 minutes, 120 minutes, 8 hours (before next dose), and 24 hours before the next morning dose (if applicable), if possible. Patients who provide consent for the PK sampling, but are no longer hospitalized on Day 7, will not have Day 7 PK samples collected.
- o. Blood samples to be obtained on Day 1 (before the first study drug administration) and Days 7, 14, 21, 28, and 60 (when possible). Blood samples for biomarkers must be collected on Days 7, 14, 21, 28, and 60 if a patient is still hospitalized. If a patient is discharged, the study site should arrange an outpatient visit (ie, at the study site) to accommodate the collection of blood samples for biomarkers on Days 7, 14, 21, 28, and 60.

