11.3. Presentation of Concentration Data

11.3.1. Handling of Missing Data

Missing concentration data for all patients who are administered study drug will be considered as noninformative missing and will not be imputed. No concentration estimates will be provided for missing sample values.

11.3.2. Handling of the Difference between the Scheduled (nominal time) and the Actual Sampling Times (actual time)

For all sampling times, the actual sampling times relative to dosing are calculated as the difference between the actual clock time of sampling and the actual clock time of dosing. The actual post-dose sampling times relative to dosing expressed in hours and rounded off to three decimal digits are used, except for pre-dose samples occurring prior to dosing, which are reported as zero (0.000), regardless of the time difference. Scheduled sampling times are presented in concentration tables. If the actual time of sampling is missing, the nominal time is used.

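### Section 11.5 runs exposure-biomarker correlations only when the scatterplots already look strong, then offers the p-value as proof that the correlation is valid

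*SAP*

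**What the plan says.** SAP Section 11.5 has two optional steps. First, plasma exposure (Cmax or AUC0-t) may be set against biomarker changes from baseline, "using Day 7 if available, may be explored applying exposure-response scatterplots". Second, "Further correlation analysis (eg, utilizing a combination of Spearman and Pearson correlation) may be applied if exposure-response scatterplots reveal any robust relationships". The output of the second step is described as follows: "Tables will be then produced for calculated correlation coefficient, confidence intervals for Pearson coefficient in addition to p-value, to demonstrate the validity of correlation". The section does not define what makes a relationship robust, list the pairs, choose between Pearson and Spearman, or give a significance level.

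Section 5.6 names seven biomarkers (CRP, IL-1β, IL-6, TNF-α, IFN-γ, D-dimer, ferritin) and leaves the list open. Section 6.5 limits the PK set to patients given active drug, and Section 4.3 expects about 20 of them in the PK subset. Section 8.1 sets a two-sided 10% level for treatment comparisons and states that multiplicity is not adjusted for.

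On Day 7 samples, Table 1 footnote n and Section 11.1 say: "Patients who provide consent for the PK sampling, but are no longer hospitalized on Day 7, will not have Day 7 PK samples collected". For the biomarkers, footnote o says that after discharge "the study site should arrange an outpatient visit (ie, at the study site) to accommodate the collection of blood samples for biomarkers". Section 11.3.1 adds: "Missing concentration data for all patients who are administered study drug will be considered as noninformative missing and will not be imputed".

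**The concern.** The plot and the test use the same 20 or so patients. If the test is run because the plot looks strong, a small p-value mostly restates that the plot looked strong. It is not independent confirmation, yet Section 11.5 gives it that role. The coefficients that reach the tables are also biased away from zero, because pairs that looked weak need never be tabulated.

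This is the only exposure-response analysis in the SAP, in a trial of one dose. A relationship described as valid could be carried into later development with more weight than the data support.

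The second question is which patients supply the Day 7 exposure. Those discharged by then have no Day 7 PK sample, although a Day 7 biomarker sample is still sought. The complete Day 7 pairs therefore come only from patients still in hospital, and the SAP neither labels the analysis that way nor counts those missing.

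**Working it through.** Section 11.5 states no figure to reproduce, so the check is on the error rate of its rule.

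**Inputs.** From the SAP: n of about 20 active PK patients at most (Sections 4.3 and 6.5). Assumed: a 5% two-sided level (none is given for the correlations); a visual screen equivalent to |r| of at least c, with c = 0.3, 0.4 or 0.5; n of 15 or 10 to represent losses before Day 7; normal data with no true correlation.

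**Critical value.** The smallest significant Pearson coefficient is r_crit = t/√(t² + n − 2), with t the 97.5% point on n − 2 degrees of freedom. For n=20: 2.101/√(2.101² + 18) = 0.444. For n=15 it is 0.514, and for n=10 it is 0.632.

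**Error rate after the screen.** Under no correlation, the probability of passing, P(|r| ≥ c), is the two-sided tail of t = c√((n − 2)/(1 − c²)). If c is below r_crit, every pair with p<0.05 also passes, so the share of passing plots with p<0.05 is 0.05/P(|r| ≥ c). If c is at or above r_crit, the share is 100%.

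For n=20:
- c=0.3: t = 0.3√(18/0.91) = 1.334; P(pass) = 0.199; share = 0.05/0.199 = 25%.
- c=0.4: t = 0.4√(18/0.84) = 1.852; P(pass) = 0.0806; share = 0.05/0.0806 = 62%.
- c=0.5: above 0.444; share = 100%.

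A simulation of 40,000 null data sets gave 25%, 61% and 100%. The simulated shares at smaller n were 18%, 35% and 86% for n=15, and 12%, 20% and 35% for n=10. At the 10% level with n=20 they were 50%, 100% and 100%. All exceed the nominal level.

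**Coefficients.** Any pair that passes shows |r| of at least c by construction, so with a true value of zero every tabulated coefficient is at least 0.3, 0.4 or 0.5 in size.

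**Removing the screen is not enough.** Seven biomarkers and two exposure measures give 14 named pairs. If all are tested at 5%, the chance of at least one false p<0.05 is 1 − 0.95^14 = 51% for independent pairs. By simulation it is 43–44% if Cmax and AUC0-t correlate 0.8, and 35–37% if the biomarkers also correlate 0.5.

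**Day 7 restriction.** In a model with exposure and biomarker change truly independent and 25–75% of patients still in hospital (all assumed), the correlation among those remaining was zero when staying depended on the biomarker alone. It was −0.12 to −0.34 when staying depended on both exposure and biomarker.

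**The case against.** The strongest reply is that the section is headed exploratory, both steps are worded as optional, Section 8.1 calls the study descriptive and openly declines multiplicity adjustment, and no endpoint or sample size rests on the result. Biomarkers are also summarised separately in Section 12. This stands and sets the severity. It does not rescue a p-value said to establish validity, which is at odds with the exploratory label.

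The trigger could also be read as global: one strong plot might release tests of all pairs. The text allows that. Reporting would still depend on the data, but the conditional rates above apply to a pair-by-pair screen.

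Three stronger readings are tempting and not supported:
- A reader might take the 30% (1 − 0.95^7) or 51% familywise figures as the size of the fault. They measure the testing of every pair at an assumed 5%, which Section 8.1 already discloses. A screen cannot raise them.
- A reader might infer that discharged patients are excluded. The SAP says only that Day 7 is used where available, and states no rule on falling back to Day 1. Their Day 7 biomarker sample is not assured either, since footnote o qualifies collection by feasibility.
- A reader might infer that the Day 7 restriction biases the correlation because hospital stay depends on inflammation. That alone produced no spurious correlation in the check. Stay must also depend on exposure, which the SAP does not show.

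**Conclusion.** The concern holds as a minor point. Section 11.5 lets the appearance of the data decide whether correlations are tested, then uses the resulting p-value as evidence of validity, which it cannot supply. The direction is certain: the error rate is above nominal and the coefficients are too large. The size rests on the assumed visual threshold, the 5% level and n: 25% to 100% at n=20, and 12% to 35% at n=10.

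On the secondary point, the absence of Day 7 PK samples after discharge is certain. How many patients this affects is unknown, and bias in the correlation is possible but not shown. Calling missing concentrations non-informative is an assumption where the cause is discharge.

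**What to change.** In Section 11.5, before unblinding:
1. List the exposure-biomarker pairs and name one primary coefficient, for example Spearman.
2. Report the coefficient and confidence interval for every listed pair, whatever its plot shows.
3. Delete the closing words that give the p-value the purpose of showing validity. Then either drop the p-values or control error across the listed pairs, for example by Holm or a false discovery rate method.
4. Label the Day 7 analysis as patients hospitalised on Day 7, and report how many active PK patients lack Day 7 exposure.
5. Add Day 1 exposure as a sensitivity analysis where it can be derived, with Day 1 and Day 7 values kept apart. It should not replace Day 7 as the main analysis: single-dose exposure is a less direct measure than steady state. Nor is it assured for the whole PK set, because Section 6.5 requires only one evaluable postdose concentration and Section 11.4 bars derivation when the pre-dose sample is missing.

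The cost is a few sentences of SAP text and some extra table rows. No new samples are needed.

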13.1. Adverse Events / Adverse Drug Reactions

All AEs will be coded using the most recent MedDRA Version.

Each AE will be assigned a grade which refers to the severity of the AE based on the Common Terminology Criteria for Adverse Events version 5.0. The Common Terminology Criteria for Adverse Events v5.0 displays grades 1 through 5 with unique clinical descriptions of the severity for each AE. Tables for the classification of the AE severity and relationship to the drug are provided in Tables 6 and 7 in Section 12.6.1 of the protocol.

When changes in the severity of an AE occur more frequently than once a day, the maximum severity for the event should be noted in the eCRF. If the severity category changes over a number of days, then those changes should be recorded separately (with distinct onset dates) in the eCRF: the assessment of an AE in several records will be called as 'episodes' of one AE.

A treatment-emergent AE (TEAE) is an AE that starts or worsens at any time after initiation of study drug until the end of the follow-up period at Day 60. Events with missing onset dates will be considered as TEAEs. If a patient experiences >1 occurrence of the same AE, the occurrence with the greatest severity and the closest association with the study drug will be used in the corresponding summary tables. In case that for one AE, several AE episodes with eg changing severity are reported, an aggregation of all respective episodes to one AE will be performed prior to summarization. The worst severity and the worst relationship will be assigned to the aggregated AE.

Listings presenting all AEs including all episodes of one AE will be produced for TEAEs and non-TEAEs with the flagging of SAEs. Listings of serious TEAEs, TEAEs leading to study drug withdrawal, and TEAEs leading to death will be presented in the table section of the outputs. Additionally, in the listing TEAEs starting in the treatment period and TEAEs starting in the follow-up period or starting after the initial treatment has stopped will be flagged

An overall summary will be provided of the number and percentage of patients reporting AEs, TEAEs, treatment-related TEAEs, serious TEAEs, treatment-related serious TEAEs, TEAEs leading to study drug withdrawal and TEAEs leading to death. In the overall summary, additionally, the number and percentage of patients with at least one severe TEAE, with at least one moderate TEAE but no severe TEAE and with only mild TEAEs will be provided. For patients with any serious TEAE and for patients with any related serious TEAE exposure-adjusted events rates will be calculated and compared between treatment groups using the risk ratio [(300 mg MP1032 BID plus SoC) / (placebo plus SoC)] with respective 95% CI. This comparison will also be performed for the rate of re-hospitalization which is considered a serious AE.

The number and percentage of patients with TEAEs / treatment-related TEAEs / serious TEAEs / and TEAEs leading to study drug withdrawal will be summarized by SOC and PT for each treatment group, and total. In these tables, the incidence of TEAEs by SOC and PT will also be included. TEAEs will also be summarized by SOC and PT for maximum intensity and maximum relationship to study drug for each treatment group and total. Additionally, separate tables of TEAEs by SOC and PT will be provided for

This document is confidential.

SAP Text Version: 2.0, 31-Aug-2022 Controlled Document ID: COLOR, Effective Date 31-Aug-2020 Filing requirements: TMF

Page 44 of 56

TEAEs starting in the treatment period and for TEAEs starting in the follow-up period or after the study drug administration has stopped.

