4.1. Brief Description

This is a Phase IIa, randomized, double-blind, placebo-controlled, multicenter, proof-of-concept study designed to assess the potential efficacy and safety of 300 mg MP1032 twice daily (BID) plus SoC versus placebo plus SoC in hospitalized adults with moderate to severe COVID-19.

Approximately 40 sites worldwide will participate in this study.

Approximately 140 patients will be screened to randomize approximately 120 patients in 2:1 ratio as follows:

- Arm A (300 mg MP1032 BID plus SoC): approximately 80 patients
- Arm B (placebo BID plus SoC): approximately 40 patients

The stratification factor for randomization will include baseline COVID-19 severity (moderate and severe) and age-class (≤65 years and >65 years). COVID-19 severity will be determined using the following criteria:

- Moderate COVID-19:
 - Positive severe acute respiratory syndrome coronavirus type 2 (SARS-CoV-2) testing by standard reverse-transcription polymerase chain reaction (RT-PCR) assay or equivalent test
 - Symptoms of moderate illness with COVID-19, which could include any symptom of mild illness or shortness of breath with exertion
 - Clinical signs suggestive of moderate illness with COVID-19, such as respiratory rate ≥20 breaths per minute, saturation of oxygen (SpO₂) >93% (on room air at sea level, if possible), heart rate ≥90 beats per minute
 - No clinical signs indicative of severe or critical COVID-19
- Severe COVID-19:
 - Positive SARS-CoV-2 testing by standard RT-PCR assay or equivalent test
 - Symptoms suggestive of severe systemic illness with COVID-19, which could include any symptom of moderate illness or shortness of breath at rest, or respiratory distress
 - Clinical signs indicative of severe systemic illness with COVID-19, such as respiratory rate ≥30 breaths per minute, heart rate ≥125 beats per minute, SpO₂ ≤93% (on room air at sea level, if possible), partial pressure of oxygen (PaO₂)/ fraction of inspired oxygen (FiO₂)<300, or diagnosed with acute respiratory distress syndrome ([ARDS] according to the Berlin definition; see Table 3 in the Protocol)
 - No criteria met for critical COVID-19

To standardize the assessment of COVID-19 severity, respiratory rate, SpO₂, and heart rate will be measured when the patient is on room air at sea level (ie, no supplemental oxygen, if possible) and at rest for at least 5 minutes. If possible, the site should collect the information from each patient at the same time each day (±1 hour).

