13.5. Physical Examination

Abnormal physical examination results will be summarized by presenting number and percentage of patients for each body system by treatment group and overall for all scheduled visits. All physical examination data will be listed for the randomized patients.

This document is confidential.

SAP Text Version: 2.0, 31-Aug-2022 Controlled Document ID: CC , Effective Date 31-Aug-2020 Filing requirements: TMF

Page 46 of 56

14. Health Economics

Not applicable.

This document is confidential.

SAP Text Version: 2.0, 31-Aug-2022 Controlled Document ID: CC , Effective Date 31-Aug-2020 Filing requirements: TMF

Page 47 of 56

15. Interim Analyses or IDMCs

There will be no interim analysis in the study.

An independent DMC will be established by the sponsor or designee to review accumulating study data at regular intervals (as per the DMC charter) throughout the study to ensure the safety of patients and review overall study conduct. Additional data may be reviewed that are related to efficacy, but the DMC will only be reviewing data for risk-benefit purposes. Members will include experts in drug safety and/or medical specialist and biostatistics, who are not participating in this study and do not have affiliation with the investigators or the sponsor. The DMC can recommend in writing to the sponsor whether to continue, modify, or stop the clinical study on the basis of safety considerations. The pre-specified study stopping rules for the trial are defined as follows:

- death (not including disease progression) in any patient in whom the cause of death is judged to be related to the study drug by investigator
- the occurrence in any patient of a SAE whose causal relationship (ie, without a plausible alternative explanation) to the study drug is judged to be related by investigator
- two occurrences of a clinically significant Grade 3 or higher laboratory abnormality assessed to be related to the study drug by investigator.

The DMC's specific duties will be fully described in a DMC charter. The list of the outputs that will be produced for the DMC will be attached to the charter. An unblinded team from Syneos Health Biostatistics will perform the analyses as described in Section 4.4 of this SAP to maintain the blinding of the study.

This document is confidential.

16. Changes from Analysis Planned in Protocol

Not applicable

This document is confidential.

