 incidence for more than 1 term is identical, they will then be sorted alphabetically. Missing
 descriptive statistics or p-values that cannot be estimated will be reported as '-'
- The percentage of patients will normally be calculated as a proportion of the number of patients
 assessed in the relevant treatment group (or overall) for the analysis set presented. However,
 careful consideration is required in many instances due to the complicated nature of selecting the
 denominator, usually the appropriate number of patients exposed. Details will be described in
 footnotes or programming notes, as necessary
- For categorical summaries (number and percentage of patients) where a patient can be included in more than one category, a footnote or programming note will be added describing whether the patient is included in the summary statistics for all relevant categories or just 1 category as well as the selection criteria
- Where a category with a subheading (such as system organ class) has to be split over more than
 one page, output the subheading followed by '(cont)' at the top of each subsequent page. The
 overall summary statistics for the subheading should only be output on the first relevant page

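### The only between-arm measure for related serious TEAEs is a ratio that has no value when placebo has no event, which is likely if such events are rare; a rate difference should stand beside it

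*SAP*

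**What the plan says.** Section 13.1 plans two kinds of summary for related serious TEAEs. The first is descriptive: "An overall summary will be provided of the number and percentage of patients reporting AEs, TEAEs, treatment-related TEAEs, serious TEAEs, treatment-related serious TEAEs" and further categories. The second is comparative: "for patients with any related serious TEAE exposure-adjusted events rates will be calculated and compared between treatment groups using the risk ratio", with the ratio given as "300 mg MP1032 BID plus SoC) / (placebo plus SoC)] with respective 95% CI". The same ratio is planned for serious TEAEs and for re-hospitalization. It is the only between-arm measure with an interval in Section 13. The interval method is not named, and nothing is said about an arm with no event.

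Section 4.1 sets the arm sizes: "Arm A (300 mg MP1032 BID plus SoC): approximately 80 patients" and "Arm B (placebo BID plus SoC): approximately 40 patients".

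The only general provision for a quantity that cannot be computed is in Section 18.2.5.2, where "descriptive statistics or p-values that cannot be estimated will be reported as" a dash.

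Section 15 lists among its stopping criteria "the occurrence in any patient of a SAE whose causal relationship (ie, without a plausible alternative explanation) to the study drug is judged" by the investigator to be related. The DMC then makes a recommendation to the sponsor. The SAP states no expected rate of related serious events.

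**The concern.** Placebo is the denominator of the ratio and also the smaller arm. If placebo has no event the ratio is undefined, and if neither arm has an event it is 0/0. Related serious events on MP1032 with none on placebo are a pattern for which a reader would want an estimate and its uncertainty, and there the stated measure gives neither. A measure or a continuity correction would then have to be chosen after the counts are known, and with sparse events the result depends heavily on that choice.

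The SAP avoids this problem elsewhere. Section 7.4 compares Day 28 mortality by a common risk difference, which still gives an estimate when one arm has no deaths.

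**Working it through.** **The plan's own figure.** Section 4.3 gives 76 + 38 = 114 patients and 83% power for 10% versus 30%, two-sided alpha 10%. The pooled rate is (76 × 0.10 + 38 × 0.30)/114 = 0.1667. The chi-square power is Φ[(0.20 − 1.645 × 0.0740)/0.0819] = Φ(0.955) = 83.0%. Allowing 5% early terminations, 114/0.95 = 120, that is 80 and 40. The figures reproduce and are not in dispute.

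**Chance of no placebo event for a given risk.** Let p be the per-patient risk of a related serious TEAE. It is an assumption, taken as equal in both arms, because the SAP gives none. P(none of 40 on placebo) = (1 − p)^40. P(none in either arm) = (1 − p)^120.

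| Assumed p | None on placebo | None in either arm |
|---|---|---|
| 0.25% | 90% | 74% |
| 0.5% | 82% | 55% |
| 1% | 67% | 30% |
| 2% | 45% | 9% |
| 3% | 30% | 2.6% |
| 5% | 13% | 0.2% |
| 10% | 1.5% | about 0 |

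The even-odds point is p = 1 − 0.5^(1/40) = 1.72%. Below it, a placebo count of zero is more likely than not.

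**Chance of no placebo event for a given total.** With equal risk, 2:1 person-time and k events in all, one per affected patient, P(none on placebo) = (2/3)^k:
- k = 2: 44%
- k = 3: 30%
- k = 4: 20%

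Drawing k patients without replacement from 80 + 40 gives 44%, 29% and 19%, practically the same.

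**The other two outcomes.** For re-hospitalization at an assumed 2% or 5% per patient, placebo has none with probability 0.98^40 = 45% or 0.95^40 = 13%. For all serious TEAEs at an assumed 10%, the figure is 0.90^40 = 1.5%.

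**What the alternatives give.** As an illustration, the table takes the simple risk difference with a Newcombe (score-based) 95% CI. It also gives the exact conditional lower limit of the ratio at 2:1 person-time. With a events on MP1032 and none on placebo, the lower limit of MP1032's share is q = 0.025^(1/a), and the limit of the ratio is q/(1 − q)/2.

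| MP1032 vs placebo | Risk difference, points (95% CI) | Ratio, lower limit |
|---|---|---|
| 0/80 vs 0/40 | 0 (−8.8 to 4.6) | none |
| 1/80 vs 0/40 | 1.25 (−7.6 to 6.7) | 0.013 |
| 2/80 vs 0/40 | 2.5 (−6.4 to 8.7) | 0.094 |
| 3/80 vs 0/40 | 3.75 (−5.4 to 10.5) | 0.21 |

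For 6 versus 0 events, q = 0.541 and the lower limit of the ratio is 0.59. In every row with a placebo count of zero the upper limit of the ratio is infinite. In the reverse case, 0 versus 1, the ratio is 0 with upper limit (0.975/0.025)/2 = 19.5.

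**The case against.** **Is a zero placebo count the expected case?** A reader might infer this from the 40 placebo patients together with the Section 15 criterion, which a single related SAE meets. The document does not support it:
- No rate of related SAEs is given, and at 3% or 5% risk the chance of a placebo zero falls to 30% or 13%.
- If observation ended at the first related SAE, that event would fall on MP1032 with probability 80/120 = 67% under equal risk. But the SAP says only that the DMC can recommend continuing, modifying or stopping, so an automatic stop is not established.
- The criterion covers SAEs without a plausible alternative explanation, a narrower set than the one tabulated. Section 8.3 imputes a missing relationship as related, and Section 13.1 takes the worst relationship across episodes of one AE.
- Patients already enrolled can add events until Day 60.

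**Is this the main inferential safety comparison, and is the safety signal lost?** Neither follows. Section 8.1 describes a descriptive proof-of-concept study and assigns statistical tests to efficacy. Counts, percentages and exposure-adjusted rates are shown by arm, and serious TEAEs are listed. A split of 3/80 versus 0/40 would be plain to see; only the formal comparison would be blank.

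**Does the alternative help?** Its intervals are wide: 3/80 versus 0/40 does not exclude equal risk, and neither does the ratio limit of 0.59 for 6 versus 0. Sparse data set that limit. The current wording does not forbid an exact interval for the ratio either. Nor does a zero count on MP1032 alone belong with the failures, since the ratio is then 0 with an exact upper limit.

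All of this stands, and it limits the reach of the point. It does not change the fact that the only stated comparison has no value in a realistic case and that the SAP does not say what replaces it.

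**Conclusion.** The point holds in conditional form. Section 13.1 relies on a single ratio that does not exist when placebo has no event. For related serious TEAEs this is more likely than not if the per-patient risk is below about 1.7%, and has probability 44%, 30% and 20% for 2, 3 and 4 events in total. These figures rest on equal risk in both arms, about 40 placebo patients, 2:1 person-time and one event per affected patient. A higher risk on MP1032 alone would leave the 1.7% threshold, read as the placebo risk, unchanged and would raise the probabilities for a given total.

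The point bites mainly on related serious TEAEs and possibly on re-hospitalization. For serious TEAEs overall, a placebo count of zero is improbable unless the risk is low. What would be lost is the between-arm estimate and its interval, not the underlying data. This is a cheap improvement worth making before unblinding. Whether the difference or the ratio should lead is a matter of preference.

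**What to change.** In Section 13.1, for related serious TEAEs and in the same table for re-hospitalization and serious TEAEs:
- Add the exposure-adjusted rate difference, MP1032 minus placebo, with a 95% CI by a named score or exact method, beside the ratio.
- State that the ratio's 95% CI is the exact conditional interval. It is reported one-sided when one arm has no event: lower limit only if placebo has none, upper limit only if MP1032 has none. State that the ratio is not estimable when neither arm has an event.

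The cost is a few lines of SAP text and code and one more line per outcome in the table. The intervals will be wide when events are sparse, and the text should not suggest otherwise.
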